#### 10.5.2 Next Generation Sequencing

DNA will be extracted using DNEasy or QiaAMP DNA tissue kits from FFPE archival tumor sections or snap-frozen biopsies of metastases, respectively. Tumor cellularity is assessed by an expert breast pathologist ([name]); specimens with  $\geq 20\%$  tumor nuclei are considered evaluable. In the few cases with paucicellular samples ( $< 20\%$  tumor cells), multiple sections were macro-dissected to achieve  $\geq 20\%$  tumor cellularity.

Subsequently, Next Generation Sequencing (NGS) will be performed using the MSK-IMPACT™ (Memorial Sloan Kettering - Integrated Mutation Profiling of Actionable Cancer Targets), a hybridization capture-based assay for targeted deep sequencing of all exons and selected introns of 341 key cancer genes in DNA from FFPE tumor sections. Custom DNA probes targeting exons and selected introns of 341 genes are synthesized using the NimbleGen SeqCap EZ library custom oligo system and biotinylated to allow for sequence enrichment by capture using streptavidin-conjugated beads. Pooled libraries containing captured DNA fragments are subsequently sequenced on the Illumina HiSeq 2500 system (rapid-run mode) as  $2 \times 100$ -bp paired-end reads.

#### 10.5.3 Guidelines for Tissue Acquisition on Biopsies of Metastatic Lesions (when applicable)

Tissue specimens, when feasible, will be collected from recurrent or metastatic lesions using standard institutional procedures. The amount of tissue collected will follow the guidelines listed below. If a patient has more than one site of disease, only one site needs to be biopsied, and the site is left to the discretion of the patient and her treating physician. If a patient is undergoing resection of a lesion for clinical reasons (i.e. wedge resection of a new lung lesion for confirmation of diagnosis or re-testing of hormone receptor and/or HER2 status, or, resection of a chest wall lesion, or, resection of a lymph node), then the patient may opt to have a portion of that tissue (roughly equivalent to the goal amount of tissue listed in the guidelines above, i.e. the equivalent of two 5-mm punch biopsies of the skin, or 3-6 18-gauge core biopsies) stored for research at the time of the procedure.

Core biopsies are always preferred over fine needle aspirates when both are technically feasible and safe. Fine needle aspirates (FNA) are acceptable and may be used for the baseline tissue sample but may not provide enough or adequate DNA for NGS.

Listed below are the goal amounts of tissue for patients who undergo core biopsy or punch biopsy, or who have either ascites fluid or pleural fluid accessible for collection. Please note that the guidelines below are for the amount of tissue to be obtained at the baseline biopsy, and are not meant to replace clinical judgment at the time the procedure is performed. Less than the goal quantity of tissue is accepted for each type of biopsy, and will be left to the clinical judgment of the physician performing the procedure.

- Breast: A goal of 3-6 core biopsy specimens will be obtained using standard institutional guidelines for a diagnostic core biopsy of a breast mass
- Skin/chest wall: A goal of one to two 5-mm punch biopsies
- Lymph node: A goal of 3-6 core biopsy specimens will be obtained using an 18-gauge needle
- Liver: A goal of 3-6 core biopsy specimens will be obtained using an 18-gauge needle
- Lung: Because of the risk of pneumothorax associated with core needle biopsies of lung nodules, no core biopsies of lung nodules will be performed on this protocol
- Bone: Because the yield of malignant tissue from bone biopsies tends to be relatively low, if a patient has another accessible site of disease (i.e. skin, lymph node, liver), that site should be biopsied preferentially. If bone is the only biopsy-accessible site, then a goal of 3-6 core biopsy specimens will be obtained using an 18-gauge needle. It is critical that every attempt be made to process a portion of the specimen without decalcification or decalcification with EDTA instead of Formic acid as the mutational analysis cannot be performed on decalcified specimens.
- Pleural Fluid: A goal of 500 mL of pleural fluid will be obtained with a standard thoracentesis procedure, with or without image guidance, according to the clinical judgment of the treating physician and clinician performing the procedure. Less than the goal amount is acceptable, and should be based upon the clinical judgment of the Investigator and the clinician performing the procedure. If more than the goal amount of fluid is obtained, then the entire specimen (with the exception of what is needed for clinical purposes, if applicable) will be stored in the tissue bank.
- Ascites fluid: A goal of 500 mL of ascites fluid will be obtained with a standard paracentesis procedure, with or without image guidance, according to the clinical judgment of the treating physician and clinician performing the procedure. Less than the goal amount is acceptable,

and should be based upon the clinical judgment of the Investigator and the clinician performing the procedure. If more than the goal amount of fluid is obtained, then the entire specimen (with the exception of what is needed for clinical purposes, if applicable) will be stored in the tissue bank.

- For patients in whom a core biopsy is not possible and who thus undergo FNA, 3 passes should be collected.

#### 10.5.4 Instructions on fresh tissue specimen handling

If feasible, at least four core biopsy specimens should be obtained:

- Two core biopsy specimens should be snap-frozen in liquid nitrogen
- Two core biopsies should be suspended in freshly prepared 10% buffered formalin
- If additional core biopsies are obtained, 1-2 cores should be snap-frozen
- If only 1 core biopsy is obtained, it should be snap-frozen in liquid nitrogen
- If only 2 core biopsies are obtained, one should be snap-frozen in liquid nitrogen and the other should be suspended in freshly prepared 10% buffered formalin
- Do not put tissue into any solution.

For patients in whom a core biopsy is not feasible and who thus undergo FNA:

- 3 passes should be collected
- All passes should be evacuated and rinsed directly into 10% buffered formalin in the same container

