- 4.1.7 Patients must have available tissue [archived formalin-fixed paraffin embedded (FFPE) blocks or fresh frozen biopsy from primary tumor or metastatic tumor biopsy] for correlative studies. Tissue source needs to be located and available at the time of registration (tissue needs to be submitted within 3 weeks of study initiation). Patients will not be able to start study drugs without tissue availability. Submission of tissue can be waived, if approved by the Study Chair in case of extraordinary/ catastrophic circumstances
- 4.1.8 Patients must have had at least one line of systemic therapy in the metastatic setting
- 4.1.9 Current use of any of the drugs listed on the Cautionary Concomitant Med list has to be approved by the Study Chair
- 4.1.10 Patients must have adequate hematologic, hepatic and renal function. All laboratory tests must be obtained within 2 weeks from study drug initiation. These include:
  - a. ANC  $\geq 1,500/\text{mm}^3$
  - b. Platelet count  $\geq 100,000/\text{mm}^3$
  - c. HgB  $\geq 9.0 \text{ g/dL}$
  - d. Creatinine clearance  $\geq 40 \text{ mL/min}/1.73 \text{ m}^2$
  - e. SGOT, SGPT  $\leq 2.5 \times \text{ULN}$  if no liver metastasis present; SGOT, SGPT  $\leq 4 \times \text{ULN}$  if liver metastasis present
  - f. Albumin  $\geq 2.0 \text{ g/dL}$
  - g. Total serum bilirubin  $\leq 1.5 \times \text{ULN}$  ( $\leq 3 \times \text{ULN}$  or direct bilirubin  $\leq 1.5 \times \text{ULN}$  if known Gilbert's syndrome)
  - h. Potassium within institutional normal limits
  - i. Phosphorus  $\leq$  institutional upper limit of normal

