## 10. CORRELATIVE/SPECIAL STUDIES

### 10.1 Overview

Correlate/ Sample	Source	Local/ On-Site Processing	Central Processing	Shipping
FGFR1 testing	FFPE from archival tumor tissue (primary or metastatic)	Submission of FFPE archival tumor tissue block OR Submission of 5 unstained slides cut at 4 microns each placed on charged (plus) slides	Yes ( FGFR1 FISH)	Freq: Same day  Temp: Ambient  Lab: VUMC
Note: Known FGFR amplification by FISH, NGS or cfDNA are acceptable for enrollment if previously done locally				
Next Generation Sequencing (NGS)	FFPE from archival tumor tissue (primary or metastatic)	Submission of FFPE archival tumor tissue OR Submission of: - 1 H&E (or an unstained 4 micron section on a plus [charged] slide) followed by, - 6 serial 20 micron peels placed in a DNase-RNAse free tube (wrapped in parafilm to exclude moisture) followed by, - 1 H&E (or an unstained 4 micron section on a plus [charged] slide) - Peels should be placed in the - 80 freezer upon receipt until extraction is to take place	Yes (DNA extraction for NGS)	Freq: Batched  Temp: Ambient  Lab: VUMC (VUMC will subsequently be responsible to batch ship to MSKCC for NGS analyses)
Whole Blood (NGS control)	Blood- 1 tube, 8 mL, PAXgene or EDTA (purple top)	-Mix by gentle inversion 8 or 10 times - Freeze and store in 20C freezer until ready to ship to MSKCC	Yes	Freq: Batched  Temp: Ambient  Lab: VUMC (VUMC will subsequently be responsible to batch ship to MSKCC for NGS analyses)

**Note:** For patients in which archival tumor is not available and a fresh tumor biopsy is obtained, the main core should be fixed for IHC analysis on site. If additional cores are collected, they can be snap-frozen and submitted as such. The invasive tumor area in the FFPE should be at least 5 mm x 5 mm and contain 20% tumor cellularity.

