#### 10.5.1 *FGFR1* Fluorescence *In Situ* Hybridization (FISH)

Patients with known (i.e. local determination of) *FGFR1-4* amplification (by NGS, cfDNA or FISH) are eligible for study participation. For patients with *FGFR1* amplification, central confirmation of *FGFR1* amplification by FISH will be performed, but will not be required for study treatment initiation. Patients without known *FGFR1* amplification can send tissue for *FGFR1* amplification screening via FISH analysis at the Vanderbilt-Ingram Cancer Center (VICC) in the CLIA-certified Vanderbilt University Medical Center Cytogenetics Laboratory. Patients with known *FGFR2-4* amplifications (by local determination of NGS, cfDNA or FISH) will not have central confirmation of amplification status by FISH due to their overall low prevalence. From the time tissue arrives at the Coordinating Center Breast Cancer Tissue Core ([name]), a turn-around time of no longer than 7 days should be expected for the FISH results to become available thus determining if a patient is eligible or not.

*FGFR1* FISH will be performed as follows: three to four- $\mu$ m tissue sections will be mounted on sialinized slides and hybridized overnight with the Zytolight SPEC *FGFR1/CEN* 8 Dual Color Probe (ZytoVision, Bremerhaven, Germany). Briefly, after deparaffinization, the slides are denatured in the presence of 10  $\mu$ l probe for 6 min at 73°C and hybridized at 37°C overnight in StatSpin (Thermobrite, Abbott Molecular, Inc.). Post-hybridization SSC washes are performed at 72°C and then the slides are stained with DAPI before analysis. Slides are analyzed with Reflected light fluorescent microscope (Olympus BX60) at 100X for hot spots. Representative images of tumor cells are captured using Cytovision software. Thirty tumor cell nuclei from hot spots or random areas are individually evaluated with the Olympus BX60 at 100X by counting green *FGFR1* and orange centromer 8 (CEN8) signals. The average of *FGFR1* copy number and the *FGFR1/CEN8* is then calculated. Tumors are considered as *FGFR1* positive ('amplified') under one of the following conditions:

- The *FGFR1/CEN8* ratio is  $\geq 2.0$ ;
- The average number of *FGFR1* signals per tumor cell nucleus is  $\geq 6^{40}$ .

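### With one biopsy core and no archival tissue, Section 10.1 fixes the core and Section 10.5.4 freezes it; following 10.5.4 rules out FGFR1 FISH by the written method

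*Combined protocol and SAP*

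**What the plan says.** Two places in the combined protocol and SAP tell sites how to handle a fresh biopsy.

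- The note in Section 10.1 covers patients whose archival tumor is unavailable. If "a fresh tumor biopsy is obtained, the main core should be fixed for IHC analysis on site", then freezing is left for what remains: "If additional cores are collected, they can be snap-frozen and submitted as such".
- Section 10.5.4 covers fresh tissue generally. It aims for at least four cores, two frozen and two in formalin. With two cores, one goes each way. With one: "If only 1 core biopsy is obtained, it should be snap-frozen in liquid nitrogen". It makes no exception for a patient without archival tissue. The same list ends with "Do not put tissue into any solution", although earlier items place cores in buffered formalin.

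Three other parts of the plan bear on the consequence.

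- Sections 3.6.3 and 10.5 plan FGFR1 FISH in all enrolled patients, and Section 2 lists it as a correlative endpoint. Section 10.5.1 describes the assay on mounted tissue sections: "Briefly, after deparaffinization, the slides are denatured".
- Criterion 4.1.7 accepts as the required tissue either an archival paraffin block or a "fresh frozen biopsy from primary tumor or metastatic tumor biopsy".
- Section 10.5.2 extracts DNA for sequencing from paraffin sections or from snap-frozen biopsies of metastases.

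**The concern.** For the patient whom the 10.1 note describes, the two instructions are opposite once there is only one core. The choice is made once, at the procedure, and cannot be reversed. It may be made differently across the coordinating center and the four other centers.

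At stake is the tissue FISH result. It has three uses: a correlative endpoint, central confirmation when FGFR1 amplification has been reported locally, and central screening when amplification is not known (Sections 3.6.3, 7.2 and 10.5.1). In a trial of 26 to 35 patients, a FISH result lost only because of how a core was handled is an avoidable gap in a small correlative data set.

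**Working it through.** No arithmetic applies to the conflict itself. The check compares the instructions and follows each to the assays.

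**Step 1: instructions by number of cores, no archival block.**

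| Obtained | Section 10.5.4 | Note in 10.1 | Fixed tissue under 10.5.4? |
|---|---|---|---|
| 4 or more cores | two frozen, two in formalin, any further 1–2 frozen | main core fixed, others may be frozen | yes |
| 2 cores | one frozen, one in formalin | main core fixed, other may be frozen | yes |
| 1 core | frozen | fixed | **no** |
| Fine needle aspirate | all passes into formalin | not addressed | yes |

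The two sections are incompatible only in the one-core row. Three cores are not spelled out in 10.5.4.

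**Step 2: can this patient be in the trial?** Yes. Criterion 4.1.7 admits a patient whose only tissue is frozen. Section 10.5.3 accepts less than the goal quantity for each biopsy type, and 10.5.4 itself provides for a single core. Section 10.5.3 also says that "the guidelines below are for the amount of tissue to be obtained at the baseline biopsy", so the biopsy guidance is not confined to later, optional samples. Section 7.1 names FGFR FISH as one purpose of a baseline biopsy.

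**Step 3: which assays remain?**

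- Core frozen (10.5.4): sequencing is possible under 10.5.2. FISH is not possible by the written method. Section 10.1 gives paraffin tissue as its source, 10.5 asks for slides where the paraffin block cannot be released, and 10.5.1 starts by removing paraffin. No frozen-tissue method is described.
- Core fixed (10.1): FISH and sequencing are both possible in principle, because both are described from paraffin material.

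On the plan's own assay descriptions, fixing keeps both routes open and freezing closes one.

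**Step 4: does one fixed core suffice?** That is not guaranteed. Section 10.5 asks for five 4-micron slides for FISH (5 × 4 = 20 microns of depth). For a small tumor area, sequencing needs six 20-micron peels and two 4-micron sections (6 × 20 + 2 × 4 = 128 microns). The total is 148 microns, from tissue with at least 20% tumor cellularity. A thin core may fall short, but a frozen core offers no FISH at all by the written method.

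**Step 5: can sequencing stand in for central screening?** Section 10.5.1 expects FISH results within 7 days of the tissue's arrival. Section 10.1 has sequencing samples batched and then batch-shipped onward, and no turnaround is given. Sequencing of the frozen core is not set up as a screening test.

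**The case against.** The best defense is that the two passages cover different situations. The 10.1 note is written for the patient without archival tissue and leaves a fixed core. Section 10.5.4 can be read as the general list for the optional research biopsy described in Section 10.5 and in the study calendar footnotes, where paraffin tissue already exists and freezing a lone core costs no FISH result. This is a sensible reading, and it is the one the plan should state. It does not remove the point. Section 10.5.4 is the section headed as handling instructions, it contains no such limit, and neither passage refers to the other.

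The 10.1 note also says that the core should be fixed, not that it must be, and it names on-site IHC rather than FISH. That is correct. It means that 10.1 does not by itself secure the FISH result; it only leaves material on which FISH could be done.

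A reader might infer that the patient's FGFR1 status would be missing altogether and the amplification requirement undermined. The documents do not support that:

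- Amplification may be established locally by sequencing, cfDNA or FISH.
- It is not required in escalation, and it is required in only 50% of the expansion cohort (criterion 4.1.6).
- Known FGFR2–4 amplification needs no central FISH, and central FGFR1 confirmation need not precede treatment (Sections 7.2 and 10.5.1).
- Frozen tissue can be sequenced, and baseline plasma is collected from all patients for cfDNA analysis (Section 10.3).

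A reader might also take the 20% of patients expected to accept a fresh biopsy (study calendar footnotes) as the share affected. That figure concerns an optional biopsy at any time before, during or after treatment. It does not count patients with one core and no archival block.

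**Conclusion.** The contradiction is real, but its reach is narrow. For a patient with no archival paraffin tissue and a single core, a site that follows 10.5.4 cannot obtain FGFR1 FISH by the method the protocol describes. The result lost is a correlative endpoint value and, depending on the patient, the central screening or confirmation result.

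The number of such patients is not given and could be zero. It is probably small, because the plan aims for 3 to 6 cores at most core-biopsy sites and already sends tissue to formalin when two cores or an aspirate are obtained.

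The conclusion assumes that the site follows 10.5.4 rather than 10.1, and that the laboratory manual, which is not among the documents, contains neither a frozen-tissue FISH method nor an overriding handling rule.

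The unqualified ban on solutions in 10.5.4 is a separate, smaller defect. Read literally, it forbids the formalin steps in its own list.

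**What to change.** In Section 10.5.4:

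1. State that when no archival paraffin tissue exists, the first or only core goes to formalin, in line with 10.1, and only further cores are frozen.
2. Keep the freeze-first rule for a single core from an optional research biopsy when the patient already has paraffin tissue.
3. Limit the instruction against placing tissue in solution to the cores that are to be frozen.

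A cross-reference between 10.1 and 10.5.4 would help, as would naming FISH and sequencing in the 10.1 note beside IHC, so that sites know which assays the fixed core must serve.

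Criterion 4.1.7 needs no change. Restricting frozen-only tissue to patients with locally known amplification would exclude patients whom criterion 4.1.6 admits: anyone in escalation, and up to half of the expansion cohort.

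The cost is a few lines of wording and a few fewer frozen single cores, hence slightly less frozen material for sequencing in those patients.

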#### 10.5.5 Tissue specimen labeling and documentation

- Label ALL specimens before freezing
- If sample comes in contact with contaminate, make note in information section of paperwork.
- Enter time core biopsy was collected on paperwork.
- Label each collection containers with Patient ID sequence number/code letter, Medical Record #, site and location of biopsy, date and time.
- If not retrieved on site by VICC CTO personnel, outside sites should ship specimens along with Tissue/Blood Registration Form directly to:

**\*\*Specimens should be mailed to arrive at VUMC from Monday 8AM through Friday 1PM\*\***

#### 10.6 Pharmacokinetics

Full pharmacokinetic (PK) sampling of erdafitinib and palbociclib in combination with fulvestrant will be performed on Days 1 and 15 of Cycles 1 and 2 in all patients participating in the phase Ib

dose escalation portion of the trial treated on the daily dosing schedule. Of note, PK samples could be obtained from additional patients if there are concerns about the PK profiling and/or clinical safety based on the available results.

The collection time of all samples must be documented in the PK Blood Collection eCRF pages. The exact time of oral erdafitinib dosing, date sample was taken and actual time of sampling must be entered on the eCRF. Any sampling problems (e.g., patient took study drug before a pre-dose sample) must be noted in the comments section of the eCRF. On days and time-points when blood samples for biomarkers and pharmacokinetics are to be performed, the pharmacokinetic sample must be drawn first. A meal record, if feasible, should be completed on the eCRF on days of PK assessment.

On the days of full pharmacokinetic sampling, patients should take their medication at the clinic. Patients who forget to postpone their dose on these days and take their medication at home will be excluded from pharmacokinetic blood sampling for that day and they should not have blood samples collected. On the days of full pharmacokinetic sampling, the exact time of any episodes of vomiting within the first 24 h post-dosing on that day must be noted in a separate section of the eCRF. Similarly, in case of any increase of stool frequency (i.e. diarrhea) within the first 24 h post-dosing on that day, this should also be documented in a separate section of the eCRF.

The days of full pharmacokinetic blood sampling should be representative of the other study days with regard to the use of the chronically administered concomitant medications. Therefore, patients taking medication chronically should be maintained on the same dose and dose schedule throughout the study period, as medically feasible. An intermittent concomitant medication should be avoided on the days of full pharmacokinetic sampling.

All pharmacokinetic blood samples will be taken by either direct venipuncture, an indwelling cannula inserted in a forearm vein, or via a port-a cath. Please refer to the **Lab Manual** for detailed instructions for the collection (including sampling schedule if an alternative dosing schedule is adopted), handling, and shipping of samples.

The sampling regimen assumes that both erdafitinib and palbociclib will be swallowed concomitantly, or less than 5 minutes apart, and that both drugs will be taken at the same time every day. When patients come for the pre-dose PK (except for Cycle 1, Day 1), the time when erdafitinib and palbociclib were taken the day before should be noted. The blood sampling regimen for determining the pharmacokinetics of erdafitinib and palbociclib is given in Table 10.5.1 and 10.5.2. If the evaluation of emerging data of erdafitinib indicates that it may be desirable to explore different doses or schedules of erdafitinib, then new cohorts of patients will be enrolled. A dosing schedule modification would be based on PK, PD and/or safety assessments. The collection time of all samples must be documented in the PK Blood Collection.

